3.1.5. Study Period Definitions

Unless stated otherwise the following are the definitions for Induction and Extended Induction treatment periods for analysis and summaries.

3.1.5.1. Induction Treatment Period

All data collected for each subject from first dose up until the earliest event between first dose at Week 8b, first dose at mWeek 0 or End of Treatment + 5 days will be presented.

3.1.5.2. Extended Induction Treatment Period

All data collected for each subject from first dose at Week 8b up until the End of Treatment + 5 days will be presented.

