The Sponsor plans to identify 1 dose for the Phase 3 dose-confirming Induction Study, guided by the results of the Phase 2b Induction Study. The Phase 3 Induction Study will not begin until an induction dose has been selected. In that study, a to-be-determined number of subjects (currently estimated as 640, but the final number will be determined after the Phase 2b Induction Study data analysis is completed) will be randomized in a 1:1 ratio to placebo or TD-1473. The Phase 3 Induction Study has the same study design as the Phase 2b Induction Study, with the exception of the number of treatment arms.

Figure 4: Phase 3 Dose-Confirming Induction Study Schema

PHASE 3 MAINTENANCE STUDY

Subjects who are considered to have achieved clinical response by adapted Mayo score (Refer to [DEFINITION OF TERMS](#)) using centrally read endoscopic subscore at either Week 8 or Week 16 during the Induction studies will continue in the Maintenance Study:

- Subjects who achieved clinical response on TD-1473 during induction at Week 8 will be re-randomized into the Maintenance Study to placebo or one of the TD-1473 doses and contribute to the primary efficacy analysis population of the Maintenance Study.
- Subjects who achieved clinical response on placebo during Induction at Week 8 will continue to receive placebo in the Maintenance Study in a blinded manner to maintain blind. However, these subjects will not be included in the primary efficacy analysis population of the Maintenance Study.
- Subjects who did not achieve clinical response by adapted Mayo score using centrally read endoscopic subscores to the first 8 weeks of induction treatment but responded at Week 16 will continue into the Maintenance Study:
 - Subjects who received 8 weeks of placebo and 8 weeks of TD-1473 80 mg will be re-randomized into the Maintenance Study to placebo or one of the TD-1473 doses and contribute to the primary efficacy analysis population of the Maintenance Study.
 - Subjects who received 16 weeks of TD-1473 during Induction will continue to receive same dose of TD-1473 in the Maintenance Study in a blinded manner to maintain blind. However, these subjects will not be included in the primary efficacy analysis population of the Maintenance Study.

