5.2. Dosage and Administration

5.2.1. TD-1473

5.2.1.1. Induction Study

Subjects will take TD-1473 tablets once daily for approximately 8 weeks. Study drug will be self-administered orally in the morning. With the exception of clinic visit days noted in the [Table 1](#) Schedule of Procedures, subjects will be instructed to take two tablets once daily at approximately the same time each morning.

TD-1473 may be taken with or without food. Results from a clinical pharmacology study in healthy subjects showed that there was minimal decrease in plasma exposure of TD-1473 (30% on average) when administered with a high fat meal, relative to fasted conditions. The impact of food on the exposure of TD-1473 is not considered to be clinically meaningful.

Subjects will be instructed to continue dosing beyond Week 8 before they return for either a Week 8b visit or maintenance Week 0 visit depending on whether clinical response was achieved according to the adapted Mayo score post Week 8. Subjects will continue to complete a daily diary to record UC symptoms and Study drug administration.

Extended Induction

Subjects who do not demonstrate clinical response at Week 8 will receive an additional 8 weeks of treatment with active drug staying on the same dose as the first 8 weeks, except those who had received placebo during the first 8 weeks will now receive TD-1473 at 80 mg. This portion of the Induction Study will not be placebo-controlled but blinding as to the specific dose of TD-1473 will be maintained. Those who demonstrate clinical response at the end of Week 16 will enter the Maintenance Study; those who do not demonstrate clinical response at Week 16 will have an EOS visit and exit the study.

Subjects will be instructed not to take their Study drug in the morning of the Week 8b visit since Study drug administration of the extended induction regimen will be in-clinic at Week 8b and Week 16. Subjects will continue to complete a daily diary to record UC symptoms and Study drug administration. Subjects will be instructed to continue dosing beyond Week 16 until they return for the mWeek 0 visit if they are deemed to have achieved clinical response from the Week 16 adapted Mayo score or until they are deemed not achieved clinical response, in which case, Study drug administration should stop.

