- b. Subjects who received placebo during the first 8 weeks will receive TD-1473 80 mg.

This portion of the Induction Study will not be placebo-controlled, but blinding as to the specific dose of TD-1473 will be maintained. Those who demonstrate clinical response at Week 16 will enter the Maintenance Study; those who do not exit the study.

The Phase 2b-Dose Finding Induction Study (Figure 2) will enroll approximately 240 subjects, randomized 1:1:1:1 to placebo or 1 of the 3 active TD-1473 doses (20 mg, 80 mg or 200 mg).

After all enrolled subjects have either completed the Week 8 visit or terminated participation prior to Week 8, an analysis of all efficacy and safety data up to Week 8 will be performed. Results from this analysis will be used to inform the dose selection for the Phase 3 dose-confirming Induction Study and the remainder of the Phase 3 Maintenance Study, which would be ongoing at that time.

[figure not shown]
Figure 2: Phase 2b Dose-Finding Induction Study

Subjects who do not demonstrate clinical response by adapted Mayo score at Week 8 with active drug will receive an additional 8 weeks of treatment staying on the same dose of TD-1473 as the first 8 weeks, and those who had received placebo during the first 8 weeks will now receive TD-1473 at 80 mg (Figure 3).

All subjects who undergo extended induction treatment will receive active drug, and thus, this portion of the Induction Study will not be placebo-controlled, but blinding as to the specific dose of TD-1473 will be maintained. During this time, at the discretion of the investigator, subjects are permitted but are not required to begin corticosteroid taper. Those who demonstrate clinical response at Week 16 will enter the Maintenance Study; those who do not demonstrate clinical response at Week 16 will have an EOS visit and exit the study.

Figure 3: Extended Induction Treatment Regimen

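### The Phase 2b SAP ends Extended Induction without the mWeek 0 stop it uses for Induction, so for Week 16 responders the period runs into Maintenance dosing

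*SAP*

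**What the plan says.** Phase 2b SAP 3.1.5 gives its two period definitions general force: "Unless stated otherwise the following are the definitions for Induction and Extended Induction treatment periods for analysis and summaries".

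- **Induction (3.1.5.1)** runs "from first dose up until the earliest event between first dose at Week 8b, first dose at mWeek 0 or End of Treatment + 5 days".
- **Extended Induction (3.1.5.2)** has a single end rule: "All data collected for each subject from first dose at Week 8b up until the End of Treatment + 5 days will be presented".

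End of Treatment is not defined in the visible text.

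SAP 1.2.1 says what follows Extended Induction: "Those who demonstrate clinical response at Week 16 will enter the Maintenance Study; those who do not exit the study". Protocol 5.2.1.1 leaves no drug-free gap for responders: "Subjects will be instructed to continue dosing beyond Week 16 until they return for the mWeek 0 visit". Protocol 3.1 then separates two groups of Week 16 responders. For one, "Subjects who received 8 weeks of placebo and 8 weeks of TD-1473 80 mg will be re-randomized into the Maintenance Study", to placebo or a TD-1473 dose. The other, who had TD-1473 for all 16 weeks, keep their dose.

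SAP Table 4 closes the Week 16 analysis window at the smaller of Extended Induction day 71 and the end date of the Extended Induction period. SAP 3.1.3 places unscheduled assessments in these windows. For laboratory tests, SAP 3.1.4 selects the latest record in a window rather than the one nearest the nominal day.

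**The concern.** The two definitions sit next to each other and do the same job, but only one stops when the next study's drug starts. Read literally, 3.1.5.2 keeps collecting data after a subject has been re-randomised. A subject who responded on 80 mg and was then allocated to placebo, 20 mg or 200 mg could contribute a value from the new treatment to the 80 mg Extended Induction results.

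What is at stake is the attribution of some safety data by dose. The laboratory rule makes this a practical risk. Protocol 7.2 asks for specified abnormal results to be rechecked within 2 to 7 days (48 to 72 hours for AST or ALT above 3 times the upper limit of normal), and mWeek 0 falls 1 to 7 days after the Week 16 visit. A recheck of an abnormal Week 16 result can therefore be taken after the switch and, as the latest record, replace the value obtained on 80 mg.

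**Working it through.** **1. Is the stop supplied elsewhere?** In Table 4, the Week 8a/8b row uses the Induction period end date, so it inherits the mWeek 0 stop from 3.1.5.1. The Week 16 row uses the Extended Induction end date, so it inherits the gap. No other visible text closes Extended Induction at mWeek 0.

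**2. Overlap of the period with Maintenance**

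Take the last Extended Induction dose as falling the day before mWeek 0, and count the mWeek 0 day itself.

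- End of Treatment = last Extended Induction dose: 5 days.
- End of Treatment = last dose of any study drug: up to 44 × 7 + 5 = 313 days.

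**3. Overlap for visit-windowed data**

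Inputs: nominal Week 16 = Extended Induction day 56 (SAP Table 4); visit window −3 to +7 days (Protocol Table 1); mWeek 0 = +1 to +7 days after Week 16 (Protocol Table 2).

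- Week 16 visit: day 53 to day 63.
- mWeek 0, day d: 53 + 1 = 54 to 63 + 7 = 70.
- Days from mWeek 0 to the day-71 cap: 71 − d + 1, which is 18 (d = 54) down to 2 (d = 70).
- On the last-study-drug-dose reading, only this cap binds: 2 to 18 days.
- On the last-Extended-Induction-dose reading, the smaller of 5 and 72 − d applies: 2 to 5 days.
- Earliest mWeek 4 visit: 54 + 28 − 3 = day 79, beyond day 71.

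On schedule, then, no Maintenance visit after mWeek 0 enters the Week 16 window. An unscheduled value can.

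**4. Subjects whose dose label can be wrong**

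Inputs: 60 placebo subjects in Phase 2b (SAP 1.5); 60% response on active and 10% declining Maintenance (Protocol 8.2); 1:1:1:1 re-randomisation before dose selection (Protocol 3.1). The documents give no placebo response rate.

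A rate can be backed out of the roughly 400 of 880 expected to be eligible for re-randomisation (Protocol 8.2.3). There are 180 + 320 = 500 active and 60 + 320 = 380 placebo subjects.

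- If the 400 is already net of decliners: (400/0.9 − 500 × 0.6) / (380 × 0.6) = 0.63 non-response, so about 37% placebo response.
- If it is not: (400 − 300) / 228 = 0.44 non-response, so about 56%.

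Re-randomised = 60 × (1 − p) × 0.60 × 0.90, and 3/4 of them leave 80 mg:

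| Placebo response p | Re-randomised | Leave 80 mg | Of these, to placebo |
|---|---|---|---|
| 20% (assumed) | 25.9 | 19.4 | 6.5 |
| 37% (implied) | 20.5 | 15.4 | 5.1 |
| 56% (implied) | 14.2 | 10.7 | 3.6 |

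The range is about 14 to 26 re-randomised and 11 to 19 leaving 80 mg.

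**5. After the fix.** With a stop at the first mWeek 0 dose, the overlap is 0 days on either reading.

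**The case against.** The strongest reply is that little depends on this definition, and most of that reply stands.

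- **Other outputs have their own cut-offs**, and SAP 3.1.5 yields to them. Concomitant medications (3.2.5) and treatment-emergent adverse events (3.7.2) run to 28 days after the last dose. Exposure for the entire study (3.7.1) uses the last drug return date. Maximum laboratory grade (3.7.3.1) is bounded through Week 16. A reader might infer that 3.1.5.2 contaminates all of these; the documents do not support that.
- **Few tables use Extended Induction as a separate cut.** Laboratory data are shown for Induction and overall. Since overall is not separately defined for them, it may inherit the period end, but the text does not say so.
- **The whole of Maintenance is unlikely to be meant.** A reader might infer that 44 weeks are swept in. SAP section 1 limits the plan to Phase 2b data and provides a separate Maintenance SAP, and 1.2.2 describes study drug for at most 16 weeks. The last Extended Induction dose is the natural meaning.
- **Not every Week 16 responder is mislabelled.** Those on TD-1473 for 16 weeks keep their dose, so their period is wrong but their dose is not.

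Scope alone does not close the gap. The same scope applied when 3.1.5.1 was written, and that section still states the mWeek 0 stop. Even on the natural meaning, about 5 days of overlap remain.

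**Conclusion.** The rule is wrong as written, with narrow reach. For Week 16 responders, Extended Induction overlaps Maintenance by about 5 days on the natural reading. On the looser reading it overlaps by more, with visit-windowed data then held only by the day-71 cap.

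Dose misattribution is possible only for placebo-then-80 mg responders: about 14 to 26 subjects, about 11 to 19 of them leaving 80 mg. These counts rest on the planning response rate applied to placebo non-responders, 10% declining, and a placebo response that is assumed or backed out. They count people at risk, not misattributed records. The Maintenance SAP reports early termination for lack of efficacy in Phase 2b, so actual numbers may be lower.

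The routes that can be shown are an unscheduled laboratory value after mWeek 0 selected for Week 16, and any overall summary that adopts the period end. The primary and key secondary endpoints are at Week 8, and Protocol 8.5.5 makes Extended Induction results descriptive, so no inferential result changes.

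**What to change.** In Phase 2b SAP 3.1.5.2, close Extended Induction at whichever comes first: the first Maintenance dose at mWeek 0, or five days after End of Treatment. Define End of Treatment there as the last Extended Induction dose. Table 4 then needs no edit, because its Week 16 row takes the corrected end date.

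The cost is one clause, one definition and one line of period derivation.

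This does not alter the adverse event and concomitant medication tables. If they too should exclude Maintenance data, add the same mWeek 0 stop to the 28-day rules in 3.7.2 and 3.2.5. That is a separate decision and should be stated either way.

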3.1.6. Actual Treatment

In the event that a subject is dispensed incorrect treatment the following rules will be used to decide actual treatment during the period (Induction, Extended Induction or overall) that the incorrect treatment was dispensed and returned.

Mean Dose	Actual Treatment
>0 mg and <=50 mg	20mg
>50 mg and <=140 mg	80mg
>140 mg	200mg

Mean dose is calculated over a period as the summation of each dose taken (where placebo is considered 0mg) and divided by total number of doses taken.

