1.2.2. Definition of Study Drugs

Study drug comprises the following (placebo and 3 doses of TD-1473):

- TD-1473 20 mg (2 x 10 mg tablets) once daily: Taken orally for up to 16 (including Extended Induction when applicable) weeks in the morning. With the exception of clinic visit days, subjects will be instructed to take two tablets once daily at approximately the same time each morning.
- TD-1473 80 mg (2 x 40 mg tablets) once daily: Taken orally for up to 16 (including Extended Induction when applicable) weeks in the morning. With the exception of clinic visit days, subjects will be instructed to take two tablets once daily at approximately the same time each morning.
- TD-1473 200 mg (2 x 100 mg tablets) once daily: Taken orally for up to 16 (including Extended Induction when applicable) weeks in the morning. With the exception of clinic visit days, subjects will be instructed to take two tablets once daily at approximately the same time each morning.
- Placebo once daily: Taken orally for up to 8 (Induction period only) weeks in the morning. With the exception of clinic visit days, subjects will be instructed to take two tablets once daily at approximately the same time each morning. Note: Subjects who do not respond on placebo during Induction Period will be switched to TD-1473 80 mg (2 x 40 mg tablets) once daily for the Extended Induction period.

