2. ANALYSIS SETS

Table 3: Analysis Sets

Analysis Set	Definition	Treatment Assignment
Screen Failures	Subjects who give informed written consent but are not randomized are considered screen failures. Screen failure subjects and the main reason for screen fail will be captured in the EDC.	N/A
Safety*	The Safety analysis set will include all subjects who received at least one dose of study drug (TD-1473 or placebo). The Safety analysis set is the primary analysis set for safety analyses.	Actual Treatment received (see Section 3.1.6)
ITT*	The Intent-to-Treat (ITT) analysis set comprises all randomized into the Phase 2b study.	Randomized treatment
Modified ITT*	The modified Intent-to-Treat (mITT) analysis set comprises all randomized subjects who receive at least one dose of study drug. The mITT set is the primary analysis set for efficacy summaries and analyses.	Randomized treatment
Modified ITT-16w*	The modified Intent-to-Treat for extended induction (mITT-16w) analysis set comprises all randomized into the Phase 2b study, who did not meet the criteria for clinical response by adapted Mayo score at Week 8, and, continued dosing during extended induction.	Randomized treatment
PP*	The Per-Protocol (PP) analysis set comprises all subjects in the mITT analysis set who complete their Week 8 visit and have no major analysis protocol deviations	Randomized treatment

- Due to confirmed data integrity violations the data for site 36044 (deviation report GCP-23) and site 38915 (deviation report GCP-11) will be excluded from all analysis sets.

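### After a dispensing error, the Phase 2b SAP's mean-dose rule can place a subject in the safety column of a dose he or she never took

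*SAP*

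**What the plan says.** Phase 2b SAP, Section 2, Table 3 groups the Safety set by "Actual Treatment received (see Section 3.1.6"). The ITT, mITT, mITT-16w and PP sets are grouped by randomized treatment.

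Section 3.1.6 has a trigger and a time frame: "In the event that a subject is dispensed incorrect treatment the following rules will be used to decide actual treatment during the period", where the period is "Induction, Extended Induction or overall) that the incorrect treatment was dispensed and returned". The measure is an average: "Mean dose is calculated over a period as the summation of each dose taken (where placebo is considered 0mg"), divided by the number of doses taken. A mean of ">0 mg and <=50 mg" is labelled 20 mg, ">50 mg and <=140 mg" is labelled 80 mg, and anything above 140 mg is labelled 200 mg.

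Two other sections bear on this. Section 1.2.2 describes a planned change of treatment: "Subjects who do not respond on placebo during Induction Period will be switched to TD-1473 80 mg". Section 3.7 then gives separate groups to the placebo Induction period and to the 80 mg Extended Induction period of subjects randomized to placebo, for the overall exposure, compliance and adverse event summaries.

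**The concern.** A subject given a wrong kit has taken two treatments. Their average describes neither, and the arms are spaced (0, 20, 80, 200 mg) so that the average of two of them often lands in the class of a third. The subject's events are then tabulated under a dose that was never in his or her hands.

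This matters because the Phase 2b study is for dose-finding and its safety tables are read by dose. Protocol Section 8.11 makes safety and tolerability of the candidate doses an explicit step in dose selection. A rule that moves exposure to a high dose into a lower column works against that purpose, even if few subjects are affected.

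**Working it through.** The plan states no figure to reproduce, so the check applies the rule as written.

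**Inputs**
- Doses 0, 20, 80 and 200 mg (Phase 2b SAP 1.2.1 and 1.2.2).
- Cut-points 50 and 140 mg, lower limit above 0 (3.1.6).
- Dispensing at Day 1, Week 2, Week 4 and Week 8b (1.4, Table 2). This gives nominal intervals of 14, 14 and 28 days in Induction (56 in all) and 56 days in Extended Induction.
- Assumptions: one treatment per dispensing interval, no missed doses, nominal visit dates.

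**Formula.** With assigned dose A, and wrong dose W taken for d days of Induction: mean = [A × (56 − d) + W × d] / 56.

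**Enumeration.** 4 arms × 3 wrong treatments × 3 kits = 36 possible single-kit errors. The label is a dose never taken in these:

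| Assigned | Wrong kit | Days | Mean (mg) | Label | Cases |
|---|---|---|---|---|---|
| Placebo | 80 mg | 14 | 80×14/56 = 20 | 20 mg | 2 |
| Placebo | 80 mg | 28 | 80×28/56 = 40 | 20 mg | 1 |
| Placebo | 200 mg | 14 | 200×14/56 = 50 | 20 mg | 2 |
| Placebo | 200 mg | 28 | 200×28/56 = 100 | 80 mg | 1 |
| 20 mg | 200 mg | 14 | (20×42 + 200×14)/56 = 65 | 80 mg | 2 |
| 20 mg | 200 mg | 28 | (20×28 + 200×28)/56 = 110 | 80 mg | 1 |
| 80 mg | Placebo | 28 | 80×28/56 = 40 | 20 mg | 1 |
| 200 mg | Placebo | 28 | 200×28/56 = 100 | 80 mg | 1 |
| 200 mg | 20 mg | 28 | (200×28 + 20×28)/56 = 110 | 80 mg | 1 |

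The total is 12 of 36. Eight of these move 200 mg exposure into the 80 or 20 mg column, and four move 80 mg exposure into the 20 mg column. The other 24 receive a dose that was taken.

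Six of the 36 means lie exactly on a cut-point. If visit windows tip them over, the two placebo cases with a 14-day 200 mg kit go to 80 mg, which was not taken either. The other four (20 with 80 mg, and 80 with 200 mg, 28-day kit, either way round) go to the other dose taken. The count of 12 does not depend on them.

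**Small exposures.** The cut-points are the midpoints (20 + 80)/2 = 50 and (80 + 200)/2 = 140, but the bottom class starts above 0 rather than at (0 + 20)/2 = 10. One 200 mg dose among 56 gives 200/56 = 3.6 mg, so a placebo subject becomes 20 mg.

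**Overall period, placebo-to-80 mg subject who also has an error**
- A 14-day 80 mg kit in Induction: (80×14 + 0×42 + 80×56)/112 = 50, label 20 mg, never taken.
- A 200 mg kit at Week 8b: (0×56 + 200×56)/112 = 100, label 80 mg, never taken.

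**The case against.** The strongest reply is that the rule will rarely be used. Dispensing runs through the RTSM system (protocol 3.5.2 and 5.5), and the documents report no errors. Twelve of 36 weights every conceivable whole-kit error equally and is not a rate in subjects. Subjects given the wrong treatment before Week 8a have a major analysis deviation (Phase 2b SAP 3.2.3) and leave the PP set, and mITT is by randomized treatment. Adverse events, dosing dates and accountability are already listed by subject (3.7.1.1 and 3.7.2). All of this stands, and it limits the point to the safety tables.

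A second reply is that any single label misattributes mixed exposure, and that the present rule at least moves every placebo subject with active exposure out of the comparator. That also stands. A plain most-days rule would lose this protection: a placebo subject with a 14-day 200 mg kit would stay in the placebo column.

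A third is that the period could mean only the days on which the wrong kit was held, in which case the mean would equal the dose taken. The parenthesis, "actual treatment during the period (Induction, Extended Induction or overall"), names the periods and does not support that reading.

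Two stronger readings are tempting. A reader might infer that every placebo non-responder is labelled 20 mg, because (0×56 + 80×56)/112 = 40. The documents do not support this: the switch is correct dispensing, so 3.1.6 does not apply, and 3.7 separates the two periods for exposure, compliance and adverse events. A reader might also infer that a subject given only placebo has no group, because the table starts above 0. Table 3 admits subjects dosed with placebo and groups them by treatment received, so such a subject is placebo. The missing row is an editorial gap.

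**Conclusion.** The point holds for dispensing errors. As written, 3.1.6 can report a misdispensed subject under a dose never taken: 12 of 36 possible single-kit errors in Induction, with the label below the highest dose taken in every one. The count rests on nominal kit lengths, full adherence and one treatment per interval. The planned switch matters only when the same subject also has a dispensing error and doses are averaged overall.

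The number of subjects affected is unknown and may be small, and no distortion of a particular safety table can be shown from the documents. The change is still worth making, because the defect is in a stated rule and is cheap to correct.

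**What to change.** Replace the mean-dose table in 3.1.6 so that the label is always a treatment the subject took:

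- Within each period, use the active dose taken on the most days, with ties to the higher dose. Use placebo only if no active dose was taken. This adds the missing placebo row and keeps the present protection of the placebo column.
- Do not average across periods. Carry each period's label into the groups of Section 3.7.
- List the adverse events of misdispensed subjects with the dose being taken at onset.

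On the same 36 cases, none is then labelled with a dose never taken. The label is below the highest dose taken in 6 (14-day kits, two cases each: 20 mg with an 80 mg kit, 20 mg with a 200 mg kit, 80 mg with a 200 mg kit). Under the current rule that number is 20: the 12 above plus 8 more (three of 20 mg with an 80 mg kit, three of 80 mg with a 200 mg kit, and one each of 80 mg with the 28-day 20 mg kit and 200 mg with the 28-day 80 mg kit).

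The cost is SAP wording and a small programming change using dosing and accountability records already collected. The downside is that a subject with mixed exposure still carries one label per period. A placebo subject with a 14-day 200 mg kit, for example, would sit in the 200 mg column with 42 days of placebo. Some events will therefore appear under a dose not being taken at onset, and the listing is there to show them.
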